10.3 Overlapping Toxicities of Ramucirumab and Nivolumab

Overlapping toxicities of the study medications include: renal failure, infusion reaction, fatigue, decreased appetite and headache.

11 ADVERSE EVENTS

11.1 Definitions of Adverse Events

11.1.1 Adverse Event (AE)

An AE is any untoward medical occurrence whether or not considered related to the study drug that appears to change in intensity during the course of the study. The following are examples of AEs:

- Unintended or unfavorable sign or symptom
- A disease temporally associated with participation in the protocol

- An intercurrent illness or injury that impairs the well-being of the subject

Hospitalization for elective surgery or routine clinical procedures that are not the result of an AE (e.g., surgical insertion of central line) should not be recorded as an AE.

Disease progression should not be recorded as an AE, unless it is attributable to the study regimen by the site investigator.

11.1.2 Laboratory Test Abnormalities

However, the following laboratory abnormalities should be documented and reported appropriately:

- any laboratory test result that is clinically significant or meets the definition of an SAE or Drug Induced Liver Injury (DILI)
- any laboratory abnormality that required the participant to have study drug discontinued or interrupted
- any laboratory abnormality that required the subject to receive specific corrective therapy.

Wherever possible, the clinical rather than laboratory term should be used by the reporting investigator (e.g., anemia versus low hemoglobin value).

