2.1.2. Secondary Objectives

- Characterize adverse effects (AE) of nivolumab in combination with ramucirumab in subjects with previously-treated mesothelioma.
- Measure progression free survival (PFS) rate at 24 weeks with the combination of the anti PD-1 agent, nivolumab and the anti VEGFR2 antibody, ramucirumab in subjects with previously-treated mesothelioma.
- Measure overall survival (OS) at 2 years after treatment with nivolumab in combination with ramucirumab in subjects with previously-treated mesothelioma.

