10.1.5 Side Effects

Please refer to the current version of the Investigator's Brochure for a complete list of adverse events.

Ramucirumab is generally well tolerated and demonstrates a favorable safety profile in comparison to traditional chemotherapy. Important identified risks for ramucirumab include, but are not limited to hypertension, proteinuria/nephrotic syndrome, arterial thrombotic events, impaired wound healing, infusion related reactions, hemorrhage, reversible posterior leukoencephalopathy syndrome, thyroid dysfunction, and gastrointestinal disorders (perforation/diarrhea).

Further details around frequency, reporting, and management of adverse events can be found in the current version of the Investigator's Brochure.

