Endocrinopathies have been observed following treatment with nivolumab. Most cases were of low or moderate grade. The events have typically been identified through either routine periodic monitoring of specific laboratories (e.g., TSH) or as part of a work-up for associated symptoms (e.g., fatigue). Events may occur within weeks of beginning treatment, but also have been noted to occur after many months (while still on treatment). More than 1 endocrine organ may be involved (e.g., hypophysitis [pituitary inflammation] may need to be evaluated at the time adrenal insufficiency or thyroid disorder is suspected). Moderate- to high-grade cases were managed with hormone replacement therapy and, in some cases, with the addition of corticosteroids. In some cases, nivolumab treatment was held until adequate hormone replacement was provided.

Skin Adverse Events

Rash and pruritus were the most common skin AEs observed following treatment with nivolumab. The rash was typically focal with a maculopapular appearance occurring on the trunk, back, or extremities. Most cases have been of low or moderate grade. In some cases, rash and pruritus resolved without intervention. Topical corticosteroids have been used for some cases of rash. Anti-histamines have been used for some cases of pruritus. More severe cases responded to systemic corticosteroids.

Renal Adverse Events

Elevated creatinine and biopsy-confirmed tubulointerstitial nephritis and allergic nephritis have been infrequently observed following treatment with nivolumab. The frequency of renal AEs may be greater with nivolumab combination therapies than with nivolumab monotherapy. Most cases were Grade 2 or 3 and based on creatinine elevation. Subjects with a history of renal cell carcinoma or prior nephrectomy did not appear to be at higher risk. Events were managed with corticosteroids and, in all cases, renal function partially or fully improved.

Neurologic Adverse Events

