12.5 Analysis of Secondary Endpoints

Characterize adverse effects (AE) of nivolumab in combination with ramucirumab in subjects with previously-treated mesothelioma.

Proportion of subjects with each grade of adverse events as defined by CTCAE v4 will be computed along with 95% confidence intervals, and reported in a tabular and descriptive manner.

Median progression free survival (PFS) and overall survival (OS) times will be computed, and PFS rates at 3, 6, and 12 months and OS rates at 2 years +/- 2 months will be calculated with associated 95% confidence intervals. Kaplan-Meier curves for each survival rate will be plotted.

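### The safety analysis counts only recorded AEs, and the laboratory reporting rule is undefined, so low-grade laboratory toxicity can be under-counted to a site-dependent degree

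*Combined protocol and SAP*

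**What the plan says.** Safety is a listed secondary objective in Section 2.1.2: "Characterize adverse effects (AE) of nivolumab in combination with ramucirumab in subjects with previously-treated mesothelioma". Its whole analysis is one sentence in Section 12.5: "Proportion of subjects with each grade of adverse events as defined by CTCAE v4 will be computed along with 95% confidence intervals". No summary of laboratory values, worst laboratory grade, shift from baseline or vital signs is planned. The DSMB list in Section 13.1 names an AE summary report and no laboratory summary, although that list is open-ended.

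Section 11.1.2 sets out which laboratory findings are reported. It begins "However, the following laboratory abnormalities should be documented and reported appropriately" and gives three criteria:

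- a judgement of significance, or SAE or DILI status: "any laboratory test result that is clinically significant or meets the definition of an SAE or Drug Induced Liver Injury (DILI");
- a finding that caused treatment to be held or stopped;
- a finding that had to be treated.

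Clinical significance is not defined and no CTCAE grade is attached to it.

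The calendar in Section 7 marks chemistries, coagulation tests, platelets/ANC/hemoglobin, urinalysis and vital signs including blood pressure for Cycle 1 and for Cycle 2 onward. Under footnote 4, thyroid tests are done every 3 cycles starting with Cycle 4.

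**The concern.** Several of the drugs' recognised harms appear first as laboratory changes. Section 10.1.5 states: "Important identified risks for ramucirumab include, but are not limited to hypertension, proteinuria/nephrotic syndrome", and thyroid dysfunction is in the same list. Section 10.2.9 describes hepatic, renal and endocrine toxicity for nivolumab and says of the endocrine events: "The events have typically been identified through either routine periodic monitoring of specific laboratories (e.g., TSH"), or else through work-up of symptoms.

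The trial measures these quantities repeatedly but analyses only what a site chose to record as an AE. A table headed by CTCAE grade invites the reader to take its Grade 1 and Grade 2 rows as the observed frequency of those grades. If recording rests on an undefined judgement, those rows partly reflect site habit. The primary endpoint is not touched; what is at stake is how accurately a listed secondary objective is reported.

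**Working it through.** The plan gives no figure on this point, so there is none to reproduce. The check has two parts.

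**1. Which graded laboratory changes can miss every criterion in Section 11.1.2?**

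The second criterion captures anything that interrupts drug, so the hold rules for drug-related events in Tables 2 and 3 (Section 6.3) show what remains.

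| Change | Hold rule | Caught by the interruption criterion? |
|---|---|---|
| Liver tests, normal baseline | nivolumab held from Grade 2 | Grade 2 and above yes; Grade 1 no |
| Liver tests, baseline in the Grade 1 range | nivolumab held from Grade 3 | Grade 3 and above yes; Grade 2 no |
| Creatinine | nivolumab held above 1.5 x ULN | yes above that limit; not below |
| Urine protein | ramucirumab held from 2 g/24 h | yes from that limit; not below |
| Other Grade 2 laboratory change | Table 3 footnote 2: no nivolumab delay | no |
| Other drug-related Grade 3 | both drugs held | yes, apart from listed exceptions |

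The Grade 3 exceptions in Table 3 (lymphopenia, leukopenia, amylase, lipase) concern tests that are not on the calendar, so they add little. The laboratory exemption in Table 2 footnote 4 lifts discontinuation for Grade 4 only.

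What can go unrecorded is therefore mainly Grade 1-2 change that the site does not call clinically significant and does not treat. Grade 3 change judged both unrelated and not significant is a smaller remainder. The second row of the table can arise in practice: Section 3.1 admits ALT and AST up to 3 x ULN, or 5 x ULN with known hepatic metastases.

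**2. How much could this move a reported rate?**

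Inputs: n = 35 from Section 12.3, taken as the safety denominator because Section 12.5 names none. The true number affected and the share flagged are assumptions; the documents give neither. Section 12.5 does not name an interval method, so exact (Clopper-Pearson) limits are used for x of n:

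lower = Beta quantile(0.025; x, n - x + 1); upper = Beta quantile(0.975; x + 1, n - x).

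Suppose 7 of 35 subjects have a given treatment-emergent graded change.

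| Flagged | Share flagged | Rate in the AE table | Exact 95% CI |
|---|---|---|---|
| 7 | 7/7 = 100% | 7/35 = 20.0% | 8.4% to 36.9% |
| 4 | 4/7 = 57% | 4/35 = 11.4% | 3.2% to 26.7% |
| 2 | 2/7 = 29% | 2/35 = 5.7% | 0.7% to 19.2% |

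For a rarer change, with an assumed true rate of 10% and 25% flagged, the chance that no case is recorded is (1 - 0.10 x 0.25)^35 = 0.975^35 = 0.41.

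The intervals in the table overlap widely. They express sampling error around whatever was recorded and do not allow for under-recording.

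**The case against.** The strongest reply is that the plan does not exclude these findings.

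- **No exclusion is stated.** Section 11.1.2 lists what should be reported and never says that nothing else may be. Its opening word points back to a sentence absent from the available text, which may simply have been lost, so nothing should rest on that. Section 6 evaluates AEs of all grades at every visit, and Section 11.1.1 defines an AE broadly. A reader might infer a plain bar on other laboratory findings; the documents do not support that. What stands is ambiguity. A list of triggers has little purpose if every graded abnormality is already reportable, and a site could defend either practice.
- **Higher grades are mostly caught.** A reader might infer that untreated Grade 3 changes vanish. Most drug-related ones require a hold and so meet the interruption criterion.
- **Blood pressure is not a laboratory test.** Section 11.1.2 does not filter it; hypertension falls under Section 11.1.1 and has its own rows in Table 2. The only point is that no blood pressure summary is planned.
- **Baseline is partly handled.** Section 11.1.1 requires a change in intensity, so an unchanged entry abnormality is not an AE. The by-grade table still does not show from what grade a subject worsened.
- **Materiality is limited.** The objective is descriptive, and the stopping rule in Section 12.2 uses only grade 5 toxicity. That is correct, and it limits the weight of the point without removing it.

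**Conclusion.** The point holds as a risk of under-counting, confined mainly to Grade 1-2 laboratory changes that require no hold. It follows from three features together: the sole safety analysis is a count of recorded AEs; laboratory recording relies on an undefined judgement or on action taken; and that rule is not reconciled with the all-grades wording in Section 6.

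A reader might conclude that laboratory harm is in fact under-reported here. The documents cannot show that. The loss is zero if sites flag everything, and the rates of 20.0%, 11.4% and 5.7% are illustrations resting on an assumed 7 affected subjects and assumed flagging shares. What can be said is that the plan does not control the loss, although most of the values needed to remove it are already scheduled every cycle. The primary analysis and the stopping rule are unaffected.

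**What to change.** Add to Section 12.5, in substance:

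- Laboratory parameters with CTCAE v4 numeric limits (ALT, AST, bilirubin, alkaline phosphatase, creatinine, glucose, sodium, potassium, calcium, hemoglobin, platelets, ANC) will be graded by program from the collected values.
- Shift tables will run from baseline to worst on-treatment grade, with the proportion of subjects (exact 95% CI) worsening by at least one grade and to Grade 3 or above.
- Urine protein, TSH and blood pressure will be shown as shifts from baseline.
- INR and aPTT will be graded in the same way, but subjects on anticoagulants, whom Section 3.1 admits, will be excluded from that display or shown separately.
- The AE table will be kept for clinical events.

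Two supporting changes are needed. First, state that these values and the local normal limits are entered in the EDC. Section 14.1 has all data entered there, but Section 14.2 requires only source documentation for procedures done as standard of care and sends a selection of those data to the EDC. Second, reconcile Section 11.1.2 with Section 6: define clinical significance for reporting purposes, and say whether a graded laboratory abnormality outside the three criteria is recorded as an AE.

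The cost is some additional data entry and programming. Reported low-grade laboratory rates may be higher than in an AE-only table. No dose, hold or other management rule changes.

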11.1.3 Serious Adverse Event (SAE)

An SAE is an adverse event that:

- Results in death. **NOTE:** Death due to disease progression should not be reported as a SAE, unless it is attributable by the site investigator to the study drug(s)
- Is life-threatening (defined as an event in which the subject was at risk of death at the time of the event; it does not refer to an event which hypothetically might have caused death if it were more severe)
- Requires inpatient hospitalization for >24 hours or prolongation of existing hospitalization. **NOTE:** Hospitalization for anticipated or protocol specified procedures such as administration of chemotherapy, central line insertion, metastasis interventional therapy, resection of primary tumor, or elective surgery, will not be considered serious adverse events.
- Results in persistent or significant disability/incapacity
- Is a congenital anomaly or birth defect
- Is an important medical event (defined as a medical event(s) that may not be immediately life-threatening or result in death or hospitalization but, based upon appropriate medical and scientific judgment, may jeopardize the subject or may require intervention (e.g., medical, surgical) to prevent one of the other serious outcomes listed in the definition above). Examples of such events include, but are not limited to, intensive treatment in an emergency room or at home for allergic bronchospasm; blood dyscrasias or convulsions not resulting in hospitalization; or the development of drug dependency or drug abuse.
 - Potential drug induced liver injury (DILI) is also considered an important medical event.
 - Suspected transmission of an infectious agent (e.g., pathogenic or nonpathogenic) via the study drug is an SAE.

- Although pregnancy is not always serious by regulatory definition, it must be handled as an SAE.
- Ramucirumab and/or nivolumab overdose. For purposes of this trial, an overdose will be defined as any dose exceeding the prescribed dose for ramucirumab and/or nivolumab by 20%.
- Any venous or arterial event leading to discontinuation of ramucirumab therapy will be considered serious and should be reported per SAE guidelines.
- Cases of RPLS must be reported per SAE guidelines.

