1. BACKGROUND AND RATIONALE

1.1. Introduction

Malignant mesothelioma is a rare yet highly aggressive cancer for which radiation and surgical therapy are typically poor options. Cisplatin in combination with pemetrexed is now a standard first-line treatment for malignant mesothelioma [1]. However, once patients fail treatment with a pemetrexed-containing regimen, there is no standard of care available.

Anti-angiogenic therapy in conjunction with standard platinum and anti-folate chemotherapy has been shown to be effective in malignant mesothelioma patients. In a recently presented multicenter study with 445 patients, Zalcman et al. showed that the addition of bevacizumab, an anti-vascular endothelial growth factor (VEGF) monoclonal antibody, to standard cisplatin and pemetrexed resulted in improved progression-free and overall survival [2]. Progression-free survival (PFS) was median 9.6 months (95% confidence interval [CI]: 8.5-10.6) in bevacizumab arm vs. 7.5 months (95% CI: 6.8-8.1) in the reference arm (adj. hazard ratio (HR) = 0.62, 95% CI [0.50-0.75], $p < 0.0001$). Overall survival was median: 18.8 months (95% CI: 15.9-22.6) vs. 16.1 months (95% CI: 14.0-17.9) for the reference arm, (adj. HR = 0.76 [95% CI: 0.61; 0.94], $p = 0.012$). Additionally, added toxicity was minimal with similar rates of G3-4 hematologic events in both arms. Hypertension, proteinuria, hemorrhage and thrombotic events were in line with previously reported rates for bevacizumab in other cancer types.

Immunotherapy of cancer became a very attractive concept after the recent introduction of checkpoint inhibitors. In a recently presented study describing the effect of a CTLA4 targeting antibody, in second line therapy of mesothelioma, 29 patients were treated with tremelimumab. The study met its primary endpoint since at a median follow-up of 14.5 months, 4 immune-related partial responses (irPR) were observed. Eleven patients had stable disease of median duration 7.7 months (range 2.6-16.6+), and the related immune-related disease control rate (irDCR) was 51.7%. Median overall survival (OS) was 11.3 months (95% CI: 5.6-17.0) [3]. The results of this study led to an ongoing “Randomized, double-blind, placebo-controlled study of tremelimumab for second- and third-line treatment of unresectable pleural or peritoneal mesothelioma” study” (NCT01843374).

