8 CRITERIA FOR DISEASE EVALUATION

A modified version of the Response Evaluation Criteria in Solid Tumors (RECIST) 1.1 will be used in this study [35]. For the purposes of this study, subjects will be reevaluated every 4 cycles (eight weeks) for 6 months, then every 6 cycles (12 weeks) until disease progression for a maximum of 2 years from initiation of study treatment. In addition to a baseline scan, confirmatory scans should also be obtained at least four weeks following initial documentation of objective response.

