10.2.9 Side Effects

Please refer to the nivolumab package insert for a complete list of adverse events. Potential safety concerns and recommended management guidelines regarding pulmonary toxicities, GI toxicities, hepatotoxicities, endocrinopathies, dermatologic toxicities, and other toxicities of concern are summarized below. Management algorithms are found in the Nivolumab IB and in Appendix 1.

The overall safety experience with nivolumab is based on experience in approximately 12,300 subjects as either monotherapy or in combination with other therapeutics. In general, for monotherapy, the safety profile is similar across tumor types. The only exception is pulmonary inflammation AEs, which may be numerically greater in subjects with NSCLC, possibly because in some cases, it can be difficult to distinguish between nivolumab-related and unrelated causes of pulmonary symptoms and radiographic changes. The most frequently reported treatment-related AE is fatigue, which is almost always of low grade.

Most related AEs are thought to be due to the effects of inflammatory cells on specific tissues. A variety of preferred terms (PTs) have been used to describe similar kinds of organ-related AEs,

with the result being that AE frequency tables organized by PTs can lead to underestimation of the frequency of similar kinds of organ-related AEs. Select AE categories group together the most common and impactful PTs by organ category. These categories include the following: pulmonary, GI, hepatic, skin, endocrine, hypersensitivity/infusion reaction, and renal AEs.

Pulmonary Adverse Events

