11.3 Sponsor-Investigator Responsibilities

HCRN will send a SAE summary to the sponsor-investigator **within 1 business day** of receipt of SAE Submission Form from a site. The sponsor-investigator will promptly review the SAE summary and assess for expectedness and relatedness.

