12.2 Criteria for Stopping Study

The study will be stopped for safety reasons if ≥ 2 subjects in first 20 or ≥ 3 in first 30 subjects develop grade 5 therapy related toxicity during first 4 cycles of therapy.

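### A death in cycles 1-4 that the site ascribes to progression need not be reviewed for relatedness by anyone else, so the only stopping rule can undercount therapy-related deaths

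*Combined protocol and SAP*

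**What the plan says.** - **Stopping rule.** Section 12.2 stops the study if at least 2 of the first 20 or at least 3 of the first 30 subjects "develop grade 5 therapy related toxicity during first 4 cycles of therapy". It does not say whose attribution decides, or which of the five relatedness categories in Section 11.1.5 count.
- **Reporting exemptions.** Section 11.1.3 exempts progression deaths from SAE reporting ("Death due to disease progression should not be reported as a SAE, unless it is attributable by the site investigator to the study drug(s"). Section 11.1.1 has the matching exemption for the AE record: "Disease progression should not be recorded as an AE, unless it is attributable to the study regimen by the site investigator".
- **Second opinion.** HCRN sends a summary to the sponsor-investigator after it receives an SAE form. Then, under Sponsor-Investigator Responsibilities (the second section numbered 11.3), "The sponsor-investigator will promptly review the SAE summary and assess for expectedness and relatedness".
- **Imaging.** After the baseline scan, Section 8 says "subjects will be reevaluated every 4 cycles (eight weeks) for 6 months". Section 8.3 recognises subjects who die before the first reassessment with no progression documented, but does not connect them to safety reporting.
- **DSMB.** Section 13.1 gives an open list that includes an adverse event summary and data for the stopping rule, reviewed at least twice a year. A listing of all deaths is not on it.

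**The concern.** The rule depends on how each early death is attributed. For a death labelled progression, the site's judgement also decides whether anyone else is asked. Other SAEs go forward whether or not they are thought related (Section 11.3.1). Progression deaths are the exception, and they are the ones most easily confused with the event that the rule counts. Section 10.2.9 says of nivolumab in NSCLC that "it can be difficult to distinguish between nivolumab-related and unrelated causes of pulmonary symptoms and radiographic changes"; carrying that over to mesothelioma is an inference, though a reasonable one for a thoracic tumour.

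The trial has one arm, so no control group would reveal an excess of early deaths. A drug-related death labelled progression would be missing from the rule's numerator and, unless a separate fatal event was recorded, from the grade 5 line of the adverse event table in Section 12.5. Both errors make the combination look safer than it is.

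**Working it through.** **Timing.** Cycles last 14 days (Section 12.1), so the rule's window is 4 x 14 = 56 days = 8 weeks. This agrees with the plan's equation of 4 cycles with eight weeks. The first scheduled on-treatment scan falls at that same point, so on schedule there are none before the window closes.

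**Route of a death in the window.**
1. If the site ascribes it to study drug, it is an SAE, the sponsor-investigator assesses relatedness, and it is available to the rule.
2. If the site ascribes it to progression and a separate serious event was reported beforehand, that event reaches the sponsor-investigator.
3. If the site ascribes it to progression and nothing separate was reported, there is no SAE form and no relatedness review, and nothing requires the DSMB to see it.

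Only route 3 is the gap.

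**Effect on the rule.** Section 12.2 gives no operating characteristics to reproduce. Let *p* be the rate of deaths counted as therapy related, X ~ Bin(20, *p*) for the first 20 subjects and Y ~ Bin(10, *p*) for the next 10. The trial continues if X = 0 and Y ≤ 2, or X = 1 and Y ≤ 1:

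P(stop) = 1 − [P(X=0)·P(Y≤2) + P(X=1)·P(Y≤1)]

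- *p* = 0.10: 1 − [0.1216 x 0.9298 + 0.2702 x 0.7361] = 1 − 0.312 = 0.688
- *p* = 0.05: 1 − [0.3585 x 0.9885 + 0.3774 x 0.9139] = 1 − 0.699 = 0.301

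If a share *s* of true therapy-related deaths is labelled as such, then *p* = true rate x *s*. Both inputs are assumptions.

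| True rate | All labelled | Three quarters | Half |
|---|---|---|---|
| 2% | 0.065 | 0.038 | 0.018 |
| 5% | 0.301 | 0.193 | 0.097 |
| 10% | 0.688 | 0.514 | 0.301 |
| 15% | 0.894 | 0.756 | 0.514 |

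**Number of early deaths, for costing the fix.** The Introduction (Section 1.1) reports, for a second-line tremelimumab study of 29 patients, a survival figure ("Median overall survival (OS) was 11.3 months (95% CI: 5.6-17.0"). With exponential survival assumed and 56 days = 1.84 months:

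P(death by week 8) = 1 − exp(−ln 2 x 1.84 / median)

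This is 0.107 at 11.3 months, 0.204 at 5.6 and 0.072 at 17.0. For 35 subjects that is 35 x 0.107 = 3.7 deaths, with a range of 2.5 to 7.1.

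**The case against.** The strongest reply is that a fatal toxicity rarely arrives unannounced. A life-threatening event, a hospitalization over 24 hours, potential liver injury or a vascular event ending ramucirumab is reportable in its own right whatever its relatedness, and a follow-up form is due on resolution. Section 8.3 separates early death and symptomatic deterioration from progression and asks for every effort to document progression objectively, so a death with no scan behind it may not qualify for the exemption at all. Unscheduled scans are not barred. The study chair confirms non-target progression (Section 8.2.3). Survival status is collected and overall survival is analysed, so the deaths are not hidden.

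Much of this stands, and it narrows the point to deaths whose whole terminal illness is labelled progression. It does not close the gap. Section 8.3 is not linked to Section 11.1.3, the chair's check covers non-target lesions only, and survival data carry no relatedness assessment.

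Three stronger readings are tempting, and the documents do not support them:
- **Progression deaths are never reported and nobody but the site reviews the rule's numerator.** The exemption has its own exception for deaths that the site attributes to study drug, every submitted SAE is reviewed for relatedness, and the DSMB's list is open and includes stopping-rule data.
- **Attributions in the window have no imaging at all.** There is a baseline scan; what is missing is a scheduled on-treatment scan before week 8.
- **Expected early deaths already sit at the thresholds.** Applying 10.7% gives about 2.1 of 20 and 3.2 of 30, but those are deaths from any cause, whereas the thresholds count therapy-related deaths only.

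**Conclusion.** The point holds in limited form. As written, the plan lets a death in cycles 1-4 leave the safety stream on the site's attribution to progression, with no required second assessment and before any scheduled on-treatment scan. The only stopping rule can therefore undercount.

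The existence of the gap rests on the text alone. Its size does not: the documents give neither a fatal-toxicity rate nor a mislabelling rate. If half of true therapy-related deaths were called progression, the chance of stopping would fall from 30% to about 10% at a 5% true rate, from 69% to 30% at 10%, and from 89% to 51% at 15%. At a 2% rate the rule seldom stops either way (6.5% against 1.8%). These figures show sensitivity to attribution; they are not estimates of what would happen. A cheap improvement is justified, but a redesign of the rule is not.

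**What to change.** - **Section 11.1.3:** require every death from first dose to the end of Cycle 4 (or to 8 weeks, if treatment stops earlier) to go to HCRN on the SAE form within 1 business day, whatever cause the site assigns. The sponsor-investigator then assesses relatedness under the existing process.
- **Section 13.1:** list all such deaths, with the site's and the sponsor-investigator's attributions side by side, for the DSMB when it reviews the Section 12.2 rule.

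Leave the thresholds unchanged. Do not add an automatic count of any death that either rater calls possibly related. With 10.7% early mortality and no true toxic deaths, that count would stop the trial with probability 33% if half of the deaths were so rated (*p* = 0.0535), or 18% if a third were (*p* = 0.0357).

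The cost is two sentences in an amendment and about 4 extra SAE forms (2.5 to 7.1 over the quoted interval), some of them for true progression deaths. The reviewers are already in place.
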